thin renal parenchyma. In addition, the presence or absence of hydroureter (proximal ureter, above the iliac bifurcation and distal ureter, below the iliac bifurcation) will be documented. If there is a stone in the renal pelvis, it will be recorded as interpolar kidney and noted as renal pelvis. For any case, if the reader believes that a particular stone is the cause of the participant's symptoms, then this will be noted. This is particularly useful in cases in which there are multiple stones. The bladder will be examined in the transverse plane at the level of the trigone to view both jets simultaneously. All participants will be scanned for 5 minutes. The number of jets from each ureteral orifice will be tabulated over time so that ureteral jet frequency, defined as number of jets per minute, can be calculated. Patients will be categorized into three groups. Group I- no ureteral jets on the symptomatic side; Group II- continuous low-level ureteral jet on the symptomatic side; Group III- ureteral jets similar to nonsymptomatic side.

In order to determine if RBUS with UJA along with clinical data confers non-inferior information compared to non-contrast CT, objective findings such as laboratory data including BMP, CBC, urine analysis and physical exam obtained as part of routine care will be retrieved from the patient's medical record and reviewed retrospectively. Clinical data and RBUS results will be de-identified/coded and the Urologist will be blinded to the CT results. Diagnosis and treatment recommendations will be determined based upon these findings and compared to those attained by CT to assess for congruence. Statistical analysis will be performed to determine non-inferiority between the studies.

Stone size and location based on CT will be recorded at the time of enrollment into the study and time to stone passage will be recorded. All study participants will be followed for stone passage. Time to stone passage will be stratified according to stone location (proximal, mid or distal ureter) and size (<2mm, 2-4mm, 5mm, 6-7mm, 9-10mm).

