7.2 Study Design

This is a single institution, prospective study to evaluate the prognostic significance of RBUS with UJA, and its utility in providing non-inferior information compared to non-contrasted CT, as well as to evaluate the spontaneous stone passage rate of ureteral stones. The study will be conducted at Washington University and will enroll approximately 100 participants over two years.

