7.3 Data Analysis

Primary objective:

This patient cohort will be analyzed retrospectively to determine whether US with UJA is predictive of spontaneous stone passage versus need for surgical intervention. Kaplan-Meier curve will be used to test time to spontaneous stone passage between the two groups. A chi-square test of independence will be used to test intervention rates between the two groups. A multivariate analysis will also be conducted controlling for such variables as age, gender, BMI, side, size of stone, and stone passage. A Cox-proportional hazards model will be used for time to spontaneous stone passage and logistic regression will be used for intervention.

Due to the unforeseen difficulty of recruitment and the uncertain assumptions of the initial power analysis, an interim statistical analysis is recommended to be performed when the recruitment reaches 50 patients. Based on the results, a decision will be made whether to continue recruitment to the initial 100 targeted patients, adjust the number of targeted patients based on a new power analysis, or to discontinue recruitment. The interim results

should not affect primary independent variables in the study as the radiologist performing the ultrasounds will not have access to the results.

Secondary objective 1:

Statistical analysis will be performed to determine diagnostic and treatment concordance between the two methods. A multivariate logistic regression model will also test patient factors that are associated with discordant results.

Secondary objective 2:

In a prospective manner, they will be followed to determine the natural history of ureteral stones with regard to stone passage. Average time to stone passage for each size category and stone location will be determined. Cox-proportional hazard models will be used to determine significant factors affecting time to stone passage.

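### The adjusted logistic model for intervention has few events per parameter, so ordinary maximum likelihood overstates the UJA odds ratio; a penalised fit with stone size in millimetres should be named

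*Combined protocol and SAP*

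**What the plan says.** Section 7.3 (Primary objective) plans an unadjusted chi-square comparison of intervention rates and then an adjusted analysis: "A multivariate analysis will also be conducted controlling for such variables as age, gender, BMI, side, size of stone, and stone passage". The models are named in the next sentence: "A Cox-proportional hazards model will be used for time to spontaneous stone passage and logistic regression will be used for intervention". The covariate list is open-ended. Section 7.3 gives no coding for UJA or stone size in this model, no choice between Wald and likelihood-ratio tests, no limit on the number of terms and no method for sparse data.

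Section 7.2 says the study "will enroll approximately 100 participants over two years", and section 7.3 adds that "an interim statistical analysis is recommended to be performed when the recruitment reaches 50 patients". On coding, section 5.2 says of UJA that "Patients will be categorized into three groups", while section 7.3 compares two groups without saying how three become two. Five size bands appear in sections 2.2, 5.2 and 7.1, but for time to stone passage: "Time to stone passage will be stratified according to stone location (proximal, mid or distal ureter) and size".

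No section states an expected number of interventions. Section 7.1 lists ED visits and hospitalization beside surgery, so the exact event behind the word intervention is also open.

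**The concern.** The precision of a logistic regression is governed by the smaller of the numbers of events and non-events, not by the number of patients. When that number is only a few times the number of coefficients, maximum likelihood pushes odds ratios away from 1, and the likelihood-ratio test no longer holds its level. If a covariate category contains no events, a coefficient runs off to infinity.

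The adjusted odds ratio is the only result planned in section 7.3 that would show whether UJA predicts intervention over and above stone size. An overstated value would make the ultrasound finding look more useful than it is. The distortion would be largest at 50 patients, where recruitment may be continued, resized or stopped, if the model is used there.

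**Working it through.** **Inputs.** From the documents: about 100 patients (7.2), a look at 50 (7.3), six named covariates plus UJA (7.3), three UJA groups (5.2) or two (7.3), and five size bands (5.2). Assumed, because the documents are silent: intervention in 15-40% of patients, a two-sided 5% level, and a true UJA odds ratio of 3 (or 1 under the null). The target of 100 cannot be reproduced, because no alpha, power, event rate or effect size is given.

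**Step 1: parameters, excluding the intercept.**
- Smallest reading: UJA 1 + (age, gender, BMI, side) 4 + size in mm 1 + the stone-passage term 1 = 7.
- Largest reading of the named list: 2 + 4 + 4 + 1 = 11.

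**Step 2: events per parameter.**
- N=100: 15/11 = 1.4 to 40/7 = 5.7.
- N=50: 7.5/11 = 0.7 to 20/7 = 2.9.
- Ceiling at any event rate (half the patients are events): 50/7 = 7.1 and 50/11 = 4.5 at N=100; 25/7 = 3.6 and 25/11 = 2.3 at N=50.

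The ceiling does not depend on the assumed rate or on how intervention is defined.

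**Step 3: effect on the estimate and the test.** This was simulated with binary UJA (40% weak or absent), age, gender, BMI, side and size as a continuous covariate. Stone passage was left out, which leaves 6 parameters. Size carries 0.7 log-odds per SD. There were 500 trials per setting, so the Monte Carlo error near 5% is about 1 point. Odds ratios are geometric means at a true value of 3; rejection rates are under a true null.

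| N | Event rate | ML odds ratio | Firth odds ratio | Wald | Likelihood-ratio | Firth penalised LR |
|---|---|---|---|---|---|---|
| 100 | 15% | 3.42 | 2.98 | 5.8% | 7.0% | 6.0% |
| 100 | 40% | 3.35 | 3.04 | 5.4% | 5.6% | 5.0% |
| 50 | 15% | 4.01 | 2.96 | 3.6% | 10.4% | 5.2% |
| 50 | 40% | 3.87 | 3.05 | 5.8% | 7.4% | 5.0% |

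A second simulation of the same 6-parameter model gave maximum-likelihood odds ratios of 3.2-3.6 at N=100 and 3.7-4.4 at N=50, against 2.9-3.0 and 2.9-3.2 with Firth. Root mean squared error was lower with Firth in every setting. The likelihood-ratio test rejected in about 6-8% and the Wald test in about 3-6%. Against 3, the overstatement is 3.2/3 to 3.6/3, or 7-20%, at N=100, and 3.7/3 to 4.4/3, or 23-47%, at N=50.

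**Step 4: failure of the fit.**
- Seven parameters, size in mm, stone passage simulated as an unrelated covariate: 0-1% at N=100 and 0-15% at N=50.
- Eleven parameters, five size bands: 22-70% at N=100 and 59-86% at N=50.
- Ten parameters with five equally filled bands: some coefficient diverges in 47-51% of fits at N=100 with 15% events, but in only 1-2% with 40% events. The UJA coefficient itself diverges in 0-9% at N=100.

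The document's own figures make empty bands plausible. Section 1.1 cites 95% passage for stones under 4 mm. If the remaining 5% had surgery, a band of 20 such patients would have no events with probability 0.95^20 = 36%, and a band of 10 with probability 0.95^10 = 60%. The bands also skip 8 mm, although section 3.1 admits stones up to 10 mm.

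**Step 5: stone passage as a covariate.** If patients who have surgery are never recorded as passing the stone, some coefficient diverges in 97-99% of fits at N=100 and 75-77% at N=50, at both event rates tried (15% and 40%). Firth still returns a finite UJA odds ratio there (3.19-3.22 at N=100), so the problem would not show in the output.

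**The case against.** The strongest reply is that this is a supporting model and that its bias at the planned size is small beside its imprecision. The chi-square test answers the primary question in section 2.1 directly and is untouched. For scale, take 25% events, 35% weak or absent jets and N=100. The expected cells are 13.6, 21.4, 11.4 and 53.6, so the unadjusted standard error of the log odds ratio is √(1/13.6 + 1/21.4 + 1/11.4 + 1/53.6) = 0.48. The bias at N=100 is ln(3.2/3) = 0.06 to ln(3.6/3) = 0.18, which is 0.14-0.38 of a standard error. That stands. It limits the size of the point but does not remove it, because the bias runs in one direction and is cheap to avoid.

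A reader might infer more than the documents support:
- **That 15-40 operations are expected.** No rate is stated, and counting ED visits or admissions could raise it. Only the ceilings in step 2 are free of that assumption.
- **That the test is too liberal.** This holds for the likelihood-ratio test. The Wald test stays near or below 5%, and section 7.3 names neither.
- **That the fit will often fail.** This needs five size bands, or stone passage as a covariate. The bands are given for time to passage; section 7.3 says only size of stone.
- **That the decision at 50 patients rests on this model.** Section 7.3 does not say which analysis is used there.
- **That the discordance model for secondary objective 1 has fewer events still.** Neither a discordance rate nor a covariate list is given.

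**Conclusion.** The concern holds in a limited form. The plan sets ordinary logistic regression a task of 7 to 11 coefficients with at most 7.1 events per parameter at N=100 and 3.6 at N=50, and includes no safeguard. The adjusted UJA odds ratio would be overstated by about 7-20% at the full sample. If the model is fitted at 50 patients, the overstatement would be about 23-47%. Likelihood-ratio tests would be mildly liberal: about 6-8% in most settings, and about 10% in one simulation at 50 patients with 15% events. With 7 parameters at N=100 non-convergence is rare; with five size bands it becomes common when events are few.

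These sizes rest on an assumed 15-40% event rate, an illustrative true odds ratio of 3, size in mm and stone passage left out. The parameter counts and the ceilings follow from the documents alone. Trouble caused by stone passage as a covariate is a separate fault in covariate choice and would occur even with many events.

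**What to change.** Add to section 7.3 that the adjusted model for intervention, at the final analysis and at the 50-patient look if it is used there, is Firth-penalised logistic regression with penalised-likelihood tests and profile-likelihood confidence intervals. Enter stone size as CT millimetres rather than in bands. State how UJA is coded and which events count as intervention, so that the parameter and event counts are fixed in advance.

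Deal separately with stone passage as a covariate in this model, since it is the competing outcome. Penalisation would hide the separation it causes, not resolve it.

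The cost is one or two sentences and standard software. The odds ratio will be slightly smaller, apparent power slightly lower, and linearity in millimetres is assumed. Penalisation does not restore precision: in the 6-parameter simulation, power for an odds ratio of 3 was 42-70% at N=100 and 21-38% at N=50.

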The prognosis of a ureteral stone as can be conveyed to the patient is based on a historical study from Miller and Kane. In 1999, the authors studied 75 patients with ureteral stones ranging from less than 2mm to 10mm over approximately 6 weeks' time. It was found that smaller, more distal stones pass sooner and that stones <4mm pass 95% of the time, although this may take up to 40 days [13]. Since that time, multiple studies have shown medical expulsive therapy (MET) to be effective for earlier stone passage [14, 15, 16]. No modern investigation of stone passage rates based on size has been performed in the MET era.

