APPENDIX A: Study Schedule of Events

		Post-Enrollment Assessment and Follow-up		
		Within one day of diagnostic CT	2 weeks post diagnostic CT (+/- 2 days)	4 weeks post diagnostic CT (+/- 2 days)
Informed Consent	X			
Incl./Excl. Criteria Confirmation	X			
RBUS with UJA	X			
Demographics¹	X			
Medical & Surgical History¹	X			
Height & Weight¹	X			
Basic metabolic panel¹	X			
Complete blood count¹	X			
Urine analysis and microscopy¹	X			
CT scan¹	X			
Assessments:				
Study related AEs/reportable events		X	X	X
Clinical stone management¹		X	X	X
Passage of stone		X	X	X

¹ as part of standard clinical care.

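### The adjusted primary analysis does not name CT stone location and lists stone passage, which is the outcome, so it need not show what UJA adds to the CT

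*Combined protocol and SAP*

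**What the plan says.** Section 7.3 (Data Analysis, primary objective) describes a multivariate analysis "controlling for such variables as age, gender, BMI, side, size of stone, and stone passage". The next sentence names the models: "A Cox-proportional hazards model will be used for time to spontaneous stone passage and logistic regression will be used for intervention". The covariates are introduced as examples. Neither stone location nor MET is among them. Side means left or right and does not stand in for proximal, mid or distal.

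The background in section 1.1 gives three determinants of passage. Of size and location it reports that "smaller, more distal stones pass sooner". Of treatment it says that "multiple studies have shown medical expulsive therapy (MET) to be effective for earlier stone passage". Only size reaches the list.

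On data, section 5.2 states: "Stone size and location based on CT will be recorded at the time of enrollment into the study". Its stated use is to stratify time to passage, which is secondary objective 2. MET appears in section 5.4 as part of clinical care. No section names a MET data item or start date. The nearest entry is "Clinical stone management" in Appendix A, which is marked at the follow-up contacts only.

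**The concern.** Jet group is observed, not assigned, and nothing in the design balances stone location across the groups. Every participant enters with a CT diagnosis, so size and location are known before the ultrasound. For these patients an adjusted model is useful because it shows whether UJA says more about outcome than the CT already does. A model with size but without location answers that only in part. If distal stones are more common in one jet group, some of the apparent UJA effect will be a location effect.

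The last item on the list is a separate fault. Stone passage is one of the two outcomes that the analysis is meant to explain. Using it as a covariate removes much of the effect that the primary objective asks about.

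Because the list is open, the covariates could also be chosen after the data are seen, and an interim analysis is planned at 50 patients.

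**Working it through.** **No design figure to reproduce.** Section 7.2 gives about 100 participants. Section 7.3 mentions an initial power analysis but shows no inputs, so the figure cannot be re-derived. The point does not depend on it.

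**1. Stone passage as a covariate.**
- *Cox model.* Passage is the event. Every event has passage = 1 and every censored patient has passage = 0. The passage coefficient then grows without limit and non-passers lose their weight in the risk sets. The UJA coefficient describes only who passed earlier among those who passed. Whether the stone passed at all no longer contributes.
- *Logistic model.* A stone that passes spontaneously generally needs no intervention. If every non-passer had intervention by day 42, passage would predict intervention perfectly and the UJA effect could not be estimated. If some non-passers had no intervention by then, the UJA coefficient would describe non-passers only.

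**2. Leaving out location: hazard ratio scale.** All inputs are assumed, with no true UJA effect. Let a and b be the distal shares in the two jet groups, and HR the hazard ratio for passage, distal v other.

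Apparent UJA hazard ratio ≈ (a·HR + 1 − a) / (b·HR + 1 − b)

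With a = 0.70, b = 0.50, HR = 2: (1.40 + 0.30) / (1.00 + 0.50) = 1.70 / 1.50 = 1.13. Equal shares give 1.00.

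The formula is the hazard ratio at the start of follow-up. I checked it against the large-sample Cox estimate with 42-day censoring. For 5% to 90% passing by day 42 the estimate is 1.13 to 1.15, so the formula does not overstate the shift.

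**3. Leaving out location: odds ratio scale.** These are separate assumptions on a different scale and do not corroborate step 2. Let p be the non-distal share, and i1 and i0 the intervention rates for non-distal and distal stones. The group rate is p·i1 + (1 − p)·i0. With p = 0.70 v 0.50:
- i1 = 0.30, i0 = 0.15: rates 0.255 and 0.225; odds ratio (0.255/0.745) / (0.225/0.775) = 1.18.
- i1 = 0.40, i0 = 0.10: rates 0.310 and 0.250; odds ratio (0.310/0.690) / (0.250/0.750) = 1.35.

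From a small imbalance (60% v 50%, first rates) to a large one (80% v 40%, second rates), the spurious odds ratio runs from 1.09 to 1.83.

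**4. MET, for scale only.** The formula of step 2 with assumed use of 80% v 50%:
- HR 1.3: 1.24/1.15 = 1.08
- HR 1.5: 1.40/1.25 = 1.12
- HR 2.0: 1.80/1.50 = 1.20

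**5. Can the model carry location?** Section 5.2 says: "Patients will be categorized into three groups". UJA therefore takes 2 parameters (section 7.3 speaks of two groups, which would take 1). Age, gender, BMI, side and size, each as one term, make 7. At 100 patients and an assumed intervention rate of 15% to 40%, there are 15 to 40 events.

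| Model | Parameters | Events per parameter |
|---|---|---|
| Listed covariates without stone passage | 7 | 15/7 = 2.1 to 40/7 = 5.7 |
| Plus distal v other | 8 | 15/8 = 1.9 to 40/8 = 5.0 |
| Plus MET (sensitivity) | 9 | 15/9 = 1.7 to 40/9 = 4.4 |

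The list as written, counting stone passage, also has 8. The exchange therefore leaves the size unchanged, but the model is thin either way.

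**The case against.** *The list is open.* This stands. Location and MET are not excluded, and an analyst could add both. The supportable fault is that nothing commits the analysis to location. An open list does not excuse stone passage, which is named. It may be a slip for another variable, but the text gives no ground for assuming which.

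*The aim is prognostic, so confounding is the wrong frame.* This largely stands. Section 2.1 asks whether UJA is predictive, and section 1.2 looks to ultrasound as an alternative to radiation. A jet pattern that partly reflects location can still predict validly where no CT is available, and the unadjusted comparison is not wrong for that question. The adjusted model asks what UJA adds to the CT. Since CT size is already listed, location belongs beside it.

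*No imbalance is shown.* This stands. A reader might infer that the UJA effect will be biased by 8% to 20% through MET or 13% through location. Those figures follow from assumed imbalances. The documents do not say that either factor differs between jet groups.

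*MET deserves the same place as location.* A reader might infer this from section 1.1, but the documents do not support it. No MET item or start date is named. Section 5.2 allows the ultrasound up to 10 days after CT, while Appendix A appears to place it within one day. A prescription on the day of the scan could come after it, and the date alone would not show the order. MET started after the scan is not a baseline covariate.

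*Secondary objective 2 needs results by MET status.* A reader might infer this from the remark in section 1.1 that passage rates by size have not been studied in the MET era. Objective 2, in sections 2.2 and 7.1, asks only about location and size. Rates pooled under current care do describe that era, and a further split of about 100 patients would leave small cells.

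**Conclusion.** The point holds in a limited form. The covariate set for the primary adjusted models is not pre-specified. It fails to name CT location, which the plan's own background links to passage and which is already recorded. It also names stone passage, which cannot serve as a covariate in either model. The stone passage fault follows from the model definitions and needs no assumed figures.

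The size of any confounding by location is unknown from the documents. At 70% v 50% distal and a hazard ratio of 2, both assumed, it is about 13%; with equal shares it is nil. MET is a weaker candidate and supports a sensitivity analysis only. The documents do not support saying that the plan excludes these variables, that the UJA estimate is biased, or that objective 2 poses a MET question.

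**What to change.** - Replace the open list in section 7.3 with a short, closed list for both models, fixed before the interim analysis at 50 patients.
- Delete stone passage from it.
- Add CT stone location, for example distal v other to limit parameters. Side may be dropped to save a parameter, but nothing else requires that.
- State that the adjusted models address what UJA adds to CT size and location, and report the unadjusted comparison beside them.
- Record from the chart the date and time of MET start relative to the ultrasound. Adjust for MET started before the scan as a sensitivity analysis only.

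The cost is SAP wording, about one parameter for location (offset by deleting stone passage) and one chart field. Location needs no new data. With so few events per parameter, the list must stay short, or the SAP should name a penalised method.

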2.0 OBJECTIVES

2.1 Primary Objective

1. To determine whether use of renal bladder ultrasound (RBUS) with UJA is predictive of spontaneous stone passage versus need for surgical intervention over a 42-day time frame.

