5.2 Study Plan and Procedures

Study RBUS with UJA will be obtained within 10 days following CT diagnosis of ureteral calculus. Ureteral jet data will be documented and patients will be followed prospectively for 42 days at 2 weeks, 4 weeks and 42 days (6 weeks) after diagnostic CT. Specifically, patients will be followed for spontaneous stone passage and will be expected to record date of stone retrieval. If specific date of stone passage is not known, date of standard of care imaging confirming absence of stone(s) will be used as the date of stone passage. If spontaneous stone passage is not achieved, patients will be counseled regarding further standard of care treatment options including surgical stone removal. If surgical intervention is indicated, time to surgical procedure will also be recorded. This patient cohort will be analyzed retrospectively to determine whether RBUS with UJA is predictive of spontaneous stone passage versus need for surgical intervention over a 42-day period.

Interpretation of RBUS and UJA:

Abdominal radiologists will interpret the RBUS research reads. All grey scale and color Doppler examinations will be performed by means of a commercially available unit with a 1-5 MHz phased array transducer or a 1-6 curved transducer. Flow toward the transducer is assigned a red color on Doppler. For grey scale evaluation, the presence or absence of urinary tract stones, size (longest axis in mm) and location- R, L, upper pole, interpolar and lower pole of the kidneys, proximal ureter, distal ureter and bladder- will be documented. The level of the renal pelvis represents the interpolar kidney with upper and lower pole above and below this level. For this study, a urinary tract stone will be termed an echogenic focus that demonstrates either posterior acoustic shadowing and or twinkle artifact on color Doppler images. In addition, presence of hydronephrosis (mild, moderate, and severe) will be documented. For the purpose of this read, hydronephrosis will be defined as such: mild hydronephrosis - urine fills the intra and extra renal pelvis and the major calyces are dilated; moderate hydronephrosis – above + dilatation of the minor calyx with preservation of the renal parenchyma; severe hydronephrosis – above +

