7.0 STATISTICAL CONSIDERATIONS

7.1 Study Objectives and Endpoints

Primary Outcome:

To determine if RBUS with UJA is prognostic of stone passage versus need for

surgical intervention:

1. Passage of stone as assessed by patient self-report and/or collection of stone or imaging.
2. Need for further medical attention as collected by chart review and phone interview for ED visit, hospitalization, or need for surgical intervention during the 42-day follow-up period.

Secondary Outcomes:

1. To determine if RBUS with UJA, in conjunction with standard of care laboratory data and history and physical confers non-inferior information compared to non-contrasted CT:
 - a. Urologist will review the patient's de-identified/coded history and physical, laboratory studies, and RBUS with UJA and make an assessment and treatment recommendations. The urologist will be blinded to the results of the CT. Comparison will be made between the CT diagnosis and the blinded assessment of the urologist.
2. To determine if the natural history and rate and time of stone passage for ureteral stones of differing locations (proximal, mid or distal ureter) and sizes (<2mm, 2-4mm, 5mm, 6-7mm, 9-10mm):
 - a. Assessment of the stone location and size to be conducted by a radiologist.

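### The chi-square and logistic analyses of intervention do not by themselves contrast stone passage with need for surgery, because a stone neither passed nor operated on by day 42 has no analysis category

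*Combined protocol and SAP*

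**What the plan says.** Section 2.1 asks whether ultrasound with ureteral jet assessment is "predictive of spontaneous stone passage versus need for surgical intervention over a 42-day time frame".

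Section 7.1 lists two components of the primary outcome. One is "Passage of stone as assessed by patient self-report and/or collection of stone or imaging". The other, covering the 42 days, is "Need for further medical attention as collected by chart review and phone interview for ED visit, hospitalization, or need for surgical intervention".

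Section 7.3 gives each side its own analysis:
- **Passage:** "Kaplan-Meier curve will be used to test time to spontaneous stone passage between the two groups", with a Cox model for the adjusted analysis.
- **Intervention:** "A chi-square test of independence will be used to test intervention rates between the two groups", and "logistic regression will be used for intervention".
- **Adjustment:** the multivariable analysis is described as "controlling for such variables as age, gender, BMI, side, size of stone, and stone passage".

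Section 5.2 recognises that some stones will not pass: "If spontaneous stone passage is not achieved, patients will be counseled regarding further standard of care treatment options including surgical stone removal". Section 5.3 finds surgery from medical records, telephone calls and procedure codes, that is, from operations carried out. No section says how a stone that is neither passed nor operated on by day 42 enters the intervention analyses.

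**The concern.** At day 42 a patient can be in one of three states: stone passed, surgery performed, or neither. The objective contrasts the first two. A test of intervention yes/no contrasts the second with everyone else, so the third state joins the passed stones unless a rule says otherwise.

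The third state is likely to occur. Section 3.1 admits stones up to 10 mm, section 1.1 says that even stones under 4 mm may take up to 40 days to pass, and section 1.2 expects larger stones to pass less often without surgery. The window is 42 days.

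It may also be unevenly spread. Section 1.2 expects weak or absent jets to mark obstruction. If so, retained stones would plausibly collect in that group and be counted on the favourable side of the intervention table.

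The covariate list raises a second issue. Stone passage is one side of the contrast that the objective poses, yet it is named as an adjustment variable. In a model for intervention it changes the question being answered.

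**Working it through.** **What can be reproduced.** The planned enrolment of about 100 (section 7.2) comes without alpha, power, effect size, event rates or group split, so it cannot be re-derived. Every rate below is assumed. The comparisons use two UJA groups because section 7.3 speaks of two, although section 5.2 defines three.

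**Step 1: the identity.** In each group, not passed = surgery + retained. So, between groups:

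difference in non-passage = difference in surgery + difference in retention.

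The surgery contrast carries the whole passage contrast only if retention does not differ between groups. The two outcomes coincide patient by patient only if no stone is retained unoperated.

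**Step 2: power at 50 v 50, two-sided 5%.** The normal approximation is

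Φ{ [ |p1 − p2| − 1.96 √(2p̄(1 − p̄)/n) ] / √([p1(1 − p1) + p2(1 − p2)]/n) }.

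For surgery 30% v 15%, p̄ = 0.225, which gives Φ{(0.150 − 0.164)/0.082} = 43%. Exact binomial enumeration of the uncorrected chi-square test gives 44%. Exact values, with surgery held at 30% v 15%:

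| Retained, weak v similar jet | Not passed | Power, surgery yes/no | Power, not passed |
|---|---|---|---|
| 25% v 10% | 55% v 25% | 44% | 88% |
| 15% v 15% | 45% v 30% | 44% | 34% |
| 10% v 20% | 40% v 35% | 44% | 8% |

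In the first row, 25/(100 − 30) = 25/70 = 36% of the weak-jet patients without intervention still hold a stone. A 30/70 group split in that row gives 42% and 82%.

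**Step 3: fix passage instead, at 60% v 80%.** By the normal approximation, non-passage has 59% power however the non-passers divide. The surgery contrast varies:
- None retained (surgery 40% v 20%): 59%.
- 10% retained in each group (30% v 10%): 71% (exact values are 73% for surgery against 60% for non-passage).
- 20% v 5% retained (20% v 15%): 9.6%.
- 25% v 5% retained (15% v 15%): no difference left to detect.

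**Step 4: the logistic model.** Take an assumed table of 100 patients:

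| | Passed | Surgery | Neither |
|---|---|---|---|
| Weak or absent jet | 30 | 10 | 10 |
| Similar jet | 40 | 8 | 2 |

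- Odds ratio for non-passage: (20/30)/(10/40) = 2.67.
- Odds ratio for intervention, passage not in the model: (10/40)/(8/42) = 1.31.
- Odds ratio for intervention, passage in the model: 0.25. This equals the fit in non-passers alone, (10/10)/(8/2).

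In the last model the passage coefficient diverges (about −25.5, standard error about 15,000), because no passer in the table had surgery. That is quasi-complete separation.

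**Step 5: the three-state test on the same table.** Expected counts per row are 35, 9 and 6. Chi-square = 2 × (25/35 + 1/9 + 16/6) = 6.98 on 2 degrees of freedom (5% critical value 5.99). For surgery yes/no, expected counts are 9 and 41, and chi-square = 2 × (1/9 + 1/41) = 0.27 on 1 degree of freedom (critical value 3.84). The full table detects a difference here that the surgery split does not.

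**The case against.** The strongest reply has four parts.

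**No stated rule.** A reader might infer that the plan scores retained stones as successes. It does not say so. Section 7.3 leaves the no-intervention category undefined, and need for surgery in sections 2.1 and 7.1 could include surgery that is indicated but not yet done. This stands: the pooling is the literal reading, supported by how section 5.3 finds surgery, and not a declared coding. It does not remove the problem, since two analysts could code the same patient differently.

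**Passage has its own analysis.** A reader might infer that the primary objective goes untested. The documents do not support that. Kaplan-Meier and Cox address time to passage, and a retained stone is unpassed there. This stands, although section 7.3 does not say how surgery is handled in those analyses. It does not change what the chi-square and logistic analyses measure.

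**The surgery rate is a legitimate outcome.** Section 1.2 hypothesises a higher rate of surgical treatment with weak or absent jets. This also stands, and it is a reason not to replace the surgery rate with passed yes/no.

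**The direction is not fixed.** It is tempting to say that the planned test always pulls the groups together. Steps 2 and 3 show that it can have less or more power than a non-passage test, depending on retention by group. The documents give no retained share, so no direction can be claimed.

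**Conclusion.** The concern holds in a limited form. The chi-square test of intervention rates does not by itself contrast passage with need for surgery. A logistic model without stone passage shares that defect. With stone passage included, the model compares surgery with retention among non-passers, can reverse the sign of the UJA effect (1.31 becomes 0.25 in the assumed table), and will separate if no passer has surgery.

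The defect is a mismatch between question and outcome, not a demonstrated loss of power. The power figures rest on assumed rates, an assumed 50 v 50 split and a two-sided 5% level. The gap between 44% and 88% requires retained stones to concentrate in the weak-jet group, and with equal 15% retention non-passage has the lower power, at 34%. These figures do not support making passed yes/no the main binary outcome. The three-state comparison does not depend on that choice.

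**What to change.** In section 7.3:
1. Define day-42 status as passed / surgery performed / neither, with unknown status as a separate class that is not merged into neither.
2. Test UJA group against this status, by chi-square on the full table or a multinomial model.
3. Report surgery and passage each as a component by UJA group. Keep the surgery rate as a reported outcome.
4. Remove stone passage from the covariates of the intervention model.
5. State that intervention means surgery performed, and how it relates to the ED visits and hospitalisations that section 7.1 groups with it.

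**Cost.** This is mainly a change of wording, since passage and surgery are already followed. There are two downsides. With two UJA groups the full table uses 2 degrees of freedom instead of 1; with three groups it uses 4 instead of 2. Also, *neither* rests partly on self-report: follow-up is by telephone (section 5.3), imaging is standard of care only (section 5.2), and no day-42 study imaging is planned. A stone passed unnoticed may therefore be hard to tell from a retained one, whereas surgery can be checked against records. The number of patients whose status rests on self-report alone should be shown beside the table.
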